#### 3.5 Secondary endpoints/outcomes

Quality of life: Sepsis, such as can be caused by cIAI relapse, impacts quality of life over a prolonged period of time. The impacts of sepsis map closely onto the components of a quality-of-life measure e.g., the EQ-5D-5L. We will therefore measure the EQ-5D-5L multiple times over the 180 days following cIAI randomisation.

Desirability Of Outcome Ranking (DOOR) [25]: Patients will be categorised according to the worst outcome they experience over the six month follow up period using a four-level ordinal classification. The four levels will be 1. No treatment failure, 2. Treatment failure (as for the primary outcome), 3. Treatment failure associated with sepsis (NEWS 6 in ward-based patients and SOFA 2 in ICU based patients [22]). Treatment failure associated with death. Note, sepsis and death must occur within 5 days of antibiotic treatment starting or changing.

Other secondary outcome measures: time to treatment failure, number of episodes of treatment failure, number and type of source control procedures, relapse of cIAI, all-cause mortality (time to event), length of hospital stay, re-admission, C. difficile infection, anti-microbial resistant (AMR) infections within 180 days of antibiotic therapy, days of antibiotic therapy (in-patient and outpatient,

including anti-fungal therapy), acute kidney injury, complications, days of ventilation and days of renal replacement therapy.

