There are three published RCTs of antibiotic durations for cIAI; STOP-IT, DURAPOP and a cIAI feasibility trial [8, 12,13]. These trials all compared different antibiotic durations and together provide a signal of efficacy for longer antibiotic treatment durations. STOP-IT reported that a median of 4 days antibiotics was as effective as a median of 8 days, with surgical-site infection, recurrent intraabdominal infection, or death occurring in 21.8% as compared with 22.3% respectively (p=0.92). However, despite the limited difference in treatment durations, the longer antibiotic durations significantly delayed time until relapse (p=<0.001), which is consistent with an incompletely treated infection. DURAPOP assessed antibiotic durations for ICU patients with cIAI and compared 8 to 15 days of antibiotics. DURAPOPs secondary outcomes reported a significantly lower rate of radiological drainage in patients treated with 15 vs. 8 days antibiotics (9%, 11/116 vs. 19%, 23/120, p=0.04). Other outcomes signalled a 15-day treatment strategy may have benefits including: median length of ICU stay (12 days vs.13 day, p=0.14), rate of bacteraemia (4% vs.11%, p=0.059) and rate of microbiological failure (16% vs. 23%, p=0.13). The cIAI feasibility trial was a 30 patient RCT conducted in Leeds, UK, and designed after consultation with a Leeds Cancer-Patient and Public Involvement (LC-PPI) group [8]. It compared 28-days antibiotics to ≤10 days for patients with cIAI. It found a relapse rate of 4/17 (24%) in the ≤10-day arm, vs. 0/13 (0%) in the 28-day arm. Infections outside the abdominal cavity were diagnosed in 6/17 (35.3%) of those in the  $\leq 10$ -day arm, vs. 1/13(7.9%) in those treated for 28-days. Current UK practice and outcomes in patients with cIAI is described by a 417-patient observational study across 30 UK hospitals [5]. In the 17.3% of patients with relapse the median time until relapse was 18 days (IQR: 13-30 days); in the 11.3% of people who died the median time to death was 23 days (IQR: 12-51 days). Antibiotic treatment had a median duration of 12 days (IQR 7-18 days). The rate of adverse events in patients treated for cIAI varies by the patients group studied. Mortality rates have been reported at up to 50% in at risk populations with severe illness, and at 10 to 20% in studies from more broad populations of patients. The need for additional source control procedures, rate of relapses and rate of treatment failure likewise varies by population and definition, being reported in 20 to 60% of patients [2,3,15-19].

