## 3.4 Primary endpoint/outcome

The primary outcome measure is: Treatment failure within 180 days of randomisation.

For in-patients, treatment failure is defined when a patient meets objective criteria for both inflammation and infection within a 5-day period. Meeting of the criteria for inflammation may precede or follow the date that criteria for infection were met (the first day of an eligible antibiotic treatment course). These criteria are:

Criteria for Inflammation

- A fever (≥ 37.8 degrees Celsius) or hypothermia (≤36 degrees Celsius), plus
- A neutrophilia (>7.5 x10^9/L) or neutropaenia (<1.8 x10^9/L), plus
- A CRP over 100 mg/L

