#### Desirability of Outcome Ranking (DOOR)

Patients will be categorised according to the worst outcome they experience over the 6 months follow up period using a four-level ordinal classification. The four levels will be  $C_1$  = No treatment failure,  $C_2$  = Treatment failure (as for the primary outcome),  $C_3$  = Treatment failure associated with sepsis and  $C_4$  = Treatment failure associated with death.

The DOOR will be analysed using a mixed effect proportional odds model with group allocation, the stratification factors and other prognostic baseline covariates included as fixed effects, with random intercepts for recruitment site. The estimated conditional odds ratio for allocation and two-sided 95% CI and p-value from this model will be reported. For i = 2, 3 and 4, risk ratios ( $Pr(Y \ge C_i | Z = Intervention, X)/Pr(Y \ge C_i | Z = Control, X)$ ) and absolute risk reductions ( $Pr(Y \ge C_i | Z = Intervention, X) - Pr(Y \ge C_i | Z = Control, X)$ ) based on the fitted model, will also be reported (with appropriate 95% confidence intervals) at various representative covariate patterns X (i.e. marginal effects at

representative values). The fitted model will also be used to compute average marginal effects of allocation on both the risk ratio and risk difference scales.

The extent to which the effect of allocation meets the proportional odds assumption will be assessed using both Brant and likelihood ratio tests (the likelihood ratio test will compare a proportional odds model with a less restrictive partial proportional odds model that allows the effect of allocation to differ across each of the three possible binary groupings of the outcome). If either of these tests suggest the effect of allocation deviates substantially from the proportional odds assumption, then the partial proportional odds model will be fitted (with cluster robust standard errors), and the three estimated odds ratios for allocation (one for each of the three possible binary groupings of the outcome) will be reported together with appropriate 95% confidence intervals and p-values [27].

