#### Number of episodes of treatment failure

The total number of episodes of treatment failure during the 180 days following randomisation will be reported descriptively by randomised group and overall. For analysis, death within 180 days following randomisation will be coded as the "worst"/"highest" outcome (i.e. death will be ranked worse than any number of treatment failure episodes without death). This outcome and its empirical cumulative distribution function will be plotted by randomised group and overall. Total number of episodes of treatment failure (with death coded as the worst/highest outcome) will be compared using a proportional odds model, with fixed effects for allocation, the stratification factors and other prognostic baseline covariates, and random intercepts for study recruitment site. This model will be used to derive marginal effects (on both the risk ratio and risk difference scales) conditional on pre-specified values of interest for the fixed effects (on both the risk ratio and risk ratio and risk difference scales) will also be reported together with appropriate 95% confidence intervals for various relevant outcomes/cut-offs.

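### DOOR puts a patient who dies within 180 days without a treatment failure episode in its best level, and a later death after failure in level 2 or 3

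*Protocol*

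**What the plan says.** Section 3.5 states the aim of DOOR: "Patients will be categorised according to the worst outcome they experience over the six month follow up period using a four-level ordinal classification". It then lists the levels: "The four levels will be 1. No treatment failure, 2. Treatment failure (as for the primary outcome), 3. Treatment failure associated with sepsis", and finally "Treatment failure associated with death". It closes with a timing rule: "Note, sepsis and death must occur within 5 days of antibiotic treatment starting or changing". Section 10.2.4 (Desirability of Outcome Ranking) repeats the aim and the four levels, without the timing rule. Its fourth level is still failure associated with death.

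Section 3.4 defines failure for in-patients: "treatment failure is defined when a patient meets objective criteria for both inflammation and infection within a 5-day period". Death enters that definition only as a substitute for the minimum antibiotic duration after a new or changed antibiotic, and the inflammation criteria must still be met. After discharge, failure requires a hospital admission.

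Section 10.2.3 codes the primary outcome as failure or no failure, with no stated rule for deaths. In 10.2.4, the analysis of the number of failure episodes takes a different line on death within 180 days: "death will be ranked worse than any number of treatment failure episodes without death". The Background gives a mortality figure from a UK observational study: "in the 11.3% of people who died the median time to death was 23 days".

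**The concern.** A ranking by worst outcome should not give its best rank to a patient who has died. Under these levels it does so whenever the death was not preceded by a qualifying failure episode. It also gives a middle rank to a patient who failed, survived the 5-day window and then died. The same patient is ranked worst in the episode-count analysis, which rests on the same failure definition.

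At stake is how DOOR is read. Its fourth level would look like mortality but hold only some of the deaths, and part of any difference in deaths between arms would be absorbed into levels 1 to 3. A related but smaller question arises for the primary outcome, where a death without a qualifying episode counts by implication as no failure.

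**Working it through.** **1. Tracing each type of death through the definitions (sections 3.4, 3.5, 10.2.3, 10.2.4)**

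| Patient | DOOR level | Primary outcome | Episode count |
|---|---|---|---|
| Dies, never met the failure criteria | 1 | No failure (implied) | Worst |
| Dies within 5 days of a new antibiotic, inflammation criteria not all met | 1 | No failure (implied) | Worst |
| Fails without sepsis, dies later with no antibiotic start or change in the last 5 days | 2 | Failure | Worst |
| Fails with sepsis in the window, dies later outside it | 3 | Failure | Worst |
| Fails, dies within 5 days of an antibiotic start or change | 4 | Failure | Worst |

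Using the 10.2.4 levels without the timing rule does not move the first two rows, because level 4 still needs failure.

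**2. How many deaths could miss level 4**

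Inputs: 583 randomised per arm (section 10.1) and 11.3% mortality (Background).

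- Expected deaths per arm: 583 × 0.113 = 65.9.
- The share outside the rule is not given. Assuming 30%, 50% or 70%: 65.9 × 0.3 = 19.8; × 0.5 = 32.9; × 0.7 = 46.1.
- As a share of the arm: 19.8/583 = 3.4% and 46.1/583 = 7.9%.

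**3. How many of these touch the primary outcome**

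Deaths after a failure are already counted as failures. Only deaths without a failure episode matter. If they are half of the deaths in step 2 (assumption): 19.8/2 = 9.9 and 46.1/2 = 23.1, so about 10 to 23 per arm (1.7% to 4.0%).

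**4. What an imbalance in deaths would do to DOOR (illustration)**

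Assumptions: failure 50% control and 40% intervention (section 10.1); deaths 11.3% control and 14.3% intervention; half of deaths outside the window; half of those without failure and half taken from level 2; sepsis in 30% of the failures not in level 4.

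- Levels 1 to 4 under the protocol rule: control 0.5000, 0.31045, 0.13305, 0.0565; intervention 0.6000, 0.22995, 0.09855, 0.0715.
- With every death in level 4: control 0.47175, 0.2822, 0.13305, 0.1130; intervention 0.56425, 0.1942, 0.09855, 0.1430.
- Probability of a better rank on intervention = Σᵢ (intervention share in level i) × (control share in worse levels + half the control share in level i).
- Result: 0.543 under the protocol rule, 0.532 with every death worst.
- With equal mortality the pair is 0.547 and 0.544. With 75% of deaths outside the window and a 6-point excess it is 0.545 and 0.516.

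**5. Effect on the sample size**

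The plan's own figure first. For 50% versus 40%, two-sided 5% and 90% power: n = (1.960 × √(2 × 0.45 × 0.55) + 1.282 × √(0.25 + 0.24))² / 0.10² ≈ 519 per arm. This is close to the stated 524, which has power 0.903. Then 524/0.9 = 582.2, so 583 per arm and 1166 in total.

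If deaths without failure (0% to 11.3% of patients, assumption) are added equally to both arms, the required number is 515 to 524 per arm and power at 524 is 0.90 to 0.905. If the intervention arm also had 3 points more such deaths, the primary outcome would still show 10 points. Failure or death would show 7 points, with power of about 62% to 63%.

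**The case against.** The strongest reply is that the plan already makes a mortality difference visible. All-cause mortality is analysed separately, with deaths by arm, survival curves and a hazard ratio. Time to failure uses cause-specific and sub-distribution hazards. In the episode-count model, being above zero is exactly failure or any death within 180 days. This stands, and it limits the harm. It does not repair DOOR, and the above-zero cut-off is not named among those to be reported.

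A second reply is that the protocol sets its death rules outcome by outcome. Days of antimicrobial therapy, ventilation and renal replacement rank death worst only in restricted circumstances. That is fair: the plan has no general rule that any death is worst, and a reader should not infer one. The conflict is narrower. It lies between DOOR's stated aim and its levels, and between DOOR and the episode count, which share a failure definition.

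A third reply is that the SAP may settle the matter. It may say how death is handled in the primary analysis, since the no-failure coding is implied and not written out. The DOOR levels and the window, however, are fixed in the protocol.

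A reader might also infer that an arm with more deaths would come out ahead because of this rule. The illustrations do not show that: DOOR favours the intervention under either rule, and the protocol rule only makes the advantage somewhat larger. Nor do all 20 to 46 deaths per arm distort the primary outcome, since those after failure already count as failures.

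**Conclusion.** The point holds for DOOR and follows from the definitions alone: a death without a failure episode is ranked best, and a death after failure but outside the window is ranked in level 2 or 3. About 20 to 46 deaths per arm (3.4% to 7.9% of patients) could be affected. That range rests on mortality from an observational cohort and on an assumed 30% to 70% of deaths outside the rule. Trial mortality may differ, since section 6.2 excludes patients likely to die within 72 hours and those with treatment limits linked to expected death.

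For the primary outcome the point is smaller. The definition implies that perhaps 10 to 23 deaths per arm count as no failure, if half of the out-of-window deaths had no episode (assumption). None of the sensitivity analyses listed in 10.2.3 addresses death. This supports one added analysis; it does not show that the primary definition is wrong. Because DOOR is a secondary outcome and mortality is reported separately, this is something that should be fixed, short of a flaw that threatens the trial's main conclusion.

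**What to change.** - In 3.5 and in the DOOR part of 10.2.4, define level 4 as death from any cause within 180 days and reserve levels 1 to 3 for survivors. Keep the 5-day window for sepsis only, and state it in both places.
- Leave the primary definition as it is. Add treatment failure or death from any cause within 180 days to the pre-specified sensitivity analyses in 10.2.3, using the same mixed logistic model.
- Report deaths without a failure episode by arm.

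The cost is a short wording change, one extra model and one extra table row. Mortality is already collected and the sample size does not change. The drawback is that deaths unrelated to the infection enter level 4. The protocol already accepts this for nights in hospital and for the number of failure episodes.

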#### 3.6. Outcome measurements

EQ-5D-5L: This questionnaire will have an initial measure taken at baseline, then follow-up questionnaires will be completed at 30, 90 and 180 days after randomisation. It will primarily be completed electronically although a paper version of the baseline questionnaire will be available for patients without access to an electronic portable device. Patients will be asked if they prefer to receive their follow-up questionnaires by email or by telephone. If they are in hospital and do not have access to a portable electronic device then a paper questionnaire will be provided. If at home, postal completion will be a back-up option. Values will be assigned by proxies for those unable to complete due to sedation or illness [23], unless they have a personal consultee (see section 7.2) who is willing to complete the questionnaire on their behalf.

Resource use questionnaire: This will collect resources used by patients when in-hospital or at home. We will include items such as, hospital stay, treating ward, hospital attendances, outpatient, GP and specialised nurse visits. We will also include items to identify use of social care resources such as social workers visits, meals on wheels or laundry services, among others. This questionnaire will be collected at the same time as the EQ-5D-5L (baseline, day 30, 90 and 180). We will aim to collect data electronically, where possible, and responses will be assigned by proxies for those unable to complete due to sedation or illness if necessary.

DOOR: Sepsis will be assessed daily as per standard practice on ICUs using the SOFA scoring system. On the ward a proxy of sepsis will be used, as SOFA scoring is not routinely completed. The proxy will be a NEWS, which is routinely recorded as part of clinical practice [22].

Number and type of source control procedures: In-patient operation notes and radiological reports will be monitored to determine the total number of source control procedures and their type (radiologically guided (Ultrasound scan, CT) or surgical (open, laparoscopic)). The definition of source control used for this study is any procedure that stops the ongoing contamination of the peritoneal cavity and removes the majority of the contaminated intraperitoneal contents to the extent that no further acute interventions are felt to be necessary. Depending on the site and origin of the infection, multiple techniques could be satisfactory to obtain source control. Acceptable procedures might include simple drainage via open, laparoscopic, or percutaneous means, repair of a perforated viscus, resection and primary re-anastomosis of a perforated viscus, resection of a perforated viscus and proximal diversion, or proximal diversion without resection as long as adequate drainage is obtained. Note, where the abdomen is left open following a surgical procedure a procedure to close the abdomen will be counted as a second and separate procedure,

Relapse of cIAI: In patients with an episode of treatment failure up to 180 days after randomisation, senior clinicians from the patient's primary care team will be asked to report if the patient had a relapse or not, and the date of the first relapse.

Antimicrobial resistant (AMR) infection: When standard treatment fails in patients with cIAI, antibiotics are often escalated to one of the carbapenem class of antibiotics. We will therefore use rates of carbapenem prescribing as a surrogate for AMR infections. Whilst all surrogates of AMR infection have limitations, this measure is important to both patients and clinicians and should be an effective AMR surrogate measure across a large number of sites.

Further, we will complete passive surveillance of AMR infection across the six month follow up period. Susceptibility patterns of bacterial isolates identified as part of routine clinical practice will be collated from microbiology laboratories to identify AMR including MRSA, VRE, ESBL and CPE. Detection of any AMR infection (MRSA, VRE, ESBL and CPE) will be a secondary outcome. Also, antimicrobial treatments will be analysed for the number of antibiotic class switches. We do not consider it feasible to standardise the investigation of infections for patients with acute infections to allow active surveillance of AMR.

Days of prescribed antibiotic therapy: Electronic medical records will be accessed to determine antibiotic (anti-bacterial) prescriptions in hospital and in the community where available. This data will be supplemented with self-reported antibiotic use at day 30, 90 and 180. Data on anti-fungal treatment will be collected to assess rates of fungal infections e.g., vulvo-vaginal candidiasis.

Others: All-cause mortality, length of hospital stay; re-admission and *C. difficile* infection will be assessed at day 180 after randomisation by review of hospital, medical records and interview with participants.

An episode of Acute Kidney Injury (Y/N): Increase in serum creatinine by  $\geq 0.3$  mg/dl ( $\geq 26.5 \mu$ mol/l) within 48 hours; or increase in serum creatinine to  $\geq 1.5$  times baseline, which is known or presumed to have occurred within the prior 7 days; or urine volume < 0.5 ml/kg/h for 6 hours (KDIGO Clinical Practice Guideline for Acute Kidney Injury).

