## 7.2.1 Method of implementing the randomisation/allocation sequence

Randomisation will occur within the first 10 days of antibiotic treatment for cIAI, and will be implemented using a web-based system designed and developed by the data management team at YTU. This system will be accessed by clinical research staff involved in patient recruitment at recruiting sites (as detailed in the site delegation log) and will be accessible 24 hours a day and 7 days a week. Prior to randomisation, research staff at recruiting sites will be required to enter the following key information; participant identification number, date of birth, participant contact details (to facilitate follow up), confirmation that the participant meets each of the eligibility criteria and the information required for stratification. The allocation sequences (one for each stratum) will be designed by the trial statistician. The actual sequences embedded in the randomisation system will be generated by a separate YTU statistician independent of the TMG, using a random number seed that will be concealed from all members of the trial team for the duration of the trial. Following randomisation, the research team at the site where the randomisation took place (including the PI, research nurses and pharmacists) will be notified of the treatment allocation by email. Each time a patient is randomised, the CI and central trial management team at YTU will also be notified by email.

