#### Source control procedures

The number, incidence and type of source control procedures occurring over the 180 days following randomisation will be reported descriptively by randomised group. The total number of source control procedures of different types (radiological, surgical) and source control procedures of any type occurring in each randomised group will be compared using a proportional odds model, with fixed effects for allocation, the stratification factors and other prognostic baseline covariates, and random intercepts for study recruitment site. This model will be used to derive the difference in mean number of source control procedures in each group, conditional on pre-specified representative values of the fixed effect covariates, as well marginal effects (on both the risk ratio and risk difference scales)

The EXTEND Trial protocol ISRCTN no. 72819021

conditional on pre-specified representative values of the fixed effect covariates (e.g. Pr(Y > 0 |Intervention, X)/Pr(Y > 0 | Control, X) for covariates X). Average marginal effects (on both the risk ratio and risk difference scales) will also be reported together with appropriate 95% confidence intervals for various relevant outcomes/cut-offs.

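### Closure of an abdomen left open before randomisation is counted as a post-randomisation source control procedure, which pulls the surgical and any-type ratio comparisons towards no effect

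*Protocol*

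**What the plan says.** Protocol section 3.6 (number and type of source control procedures) defines source control as "any procedure that stops the ongoing contamination of the peritoneal cavity and removes the majority of the contaminated intraperitoneal contents". A second condition sets how far this must go: "to the extent that no further acute interventions are felt to be necessary". The examples given there include the following: "Acceptable procedures might include simple drainage via open, laparoscopic, or percutaneous means, repair of a perforated viscus". They go on to resection and diversion. Closing the abdominal wall is not listed. The paragraph ends with a counting note for an abdomen left open after surgery: "a procedure to close the abdomen will be counted as a second and separate procedure".

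Section 10.2.4 (Source control procedures) sets the window: "The number, incidence and type of source control procedures occurring over the 180 days following randomisation". Radiological, surgical and any-type totals are compared between arms with a proportional odds model. That model also yields a difference in mean counts and contrasts in the probability of at least one procedure, Pr(Y > 0).

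Section 7.2.1 gives the timing: "Randomisation will occur within the first 10 days of antibiotic treatment for cIAI". Section 7.2 stratifies by surgical source control and by ICU stay, so some participants will already have been operated on when they are randomised.

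**The concern.** The counting note adds to the outcome a procedure that, taken alone, the outcome's own definition does not cover. Closing the abdominal wall neither stops contamination nor removes contaminated contents.

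The counting window makes this matter. A participant whose abdomen was left open at an operation before randomisation, and closed after it, scores Y of at least 1 even if recovery is uneventful. Allocation to an antibiotic duration cannot change the fact that the abdomen was already open. Neither section 3.6 nor section 10.2.4 excludes or separates such closures. Section 3.6 types procedures only as radiologically guided or surgical, so a closure would be recorded as surgical. Adjusting for surgical source control and ICU stay does not identify an open abdomen.

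At stake is how one secondary outcome is read. A count meant to show a need for further source control would also contain the completion of an operation begun before allocation.

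**Working it through.** **The protocol's own figure.** Section 10.1 gives no rate, effect or power for the source control outcome. Its only calculation is for treatment failure: 50% v 40%, two-sided 5%, 90% power. The usual two-proportion formula with pooled variance gives 519 per arm, against 524 stated. Power at 524 per arm is 90.3%. With 10% attrition, 524 / 0.9 = 582.2, rounded up to 583 per arm, or 1166. The sample size reproduces and is not affected by this point.

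**Which counts are exposed.** Closure is an operation, so it enters the surgical and any-type totals. It cannot enter the radiological total.

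**Model for Pr(Y > 0).** Let p be the proportion with a genuine later procedure. Let c be the share of each arm with a closure after randomisation of an abdomen left open before it, equal in both arms and independent of p. Then:

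- Pr(Y > 0) = p + c(1 − p)
- risk difference = (1 − c)(p1 − p0)
- risk ratio = [p1 + c(1 − p1)] / [p0 + c(1 − p0)]

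**Inputs.** 524 per arm and two-sided 5% are from section 10.1. The rates p0 = 19% and p1 = 12%, and the shares c = 3%, 5% and 10%, are assumptions. The protocol gives no value for any of them.

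For c = 5%: control 0.19 + 0.05 × 0.81 = 0.2305; intervention 0.12 + 0.05 × 0.88 = 0.1640; risk ratio 0.1640 / 0.2305 = 0.71.

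| c | Control | Intervention | Risk difference | Risk ratio | Odds ratio | Power |
|---|---|---|---|---|---|---|
| 0 | 19.0% | 12.0% | −7.0 points | 0.63 | 0.58 | 88% |
| 3% | 21.4% | 14.6% | −6.8 points | 0.68 | 0.63 | 82% |
| 5% | 23.1% | 16.4% | −6.7 points | 0.71 | 0.65 | 77% |
| 10% | 27.1% | 20.8% | −6.3 points | 0.77 | 0.71 | 67% |

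**Other assumed rates.** With 20% v 13%, power falls from 86% at c = 0 to 82% at 2% and 66% at 10%. With 30% v 21%, it falls from 92% to 90% and 80%. The direction is the same; the loss depends on c and on the rates.

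**Mean counts.** Take assumed means of 0.30 and 0.21 procedures per participant and add c to both. The difference is (0.21 + c) − (0.30 + c) = −0.09 for every c. The ratio of means moves from 0.70 at c = 0 to 0.31 / 0.40 = 0.78 at c = 10%. The expected difference is therefore not diluted, though the added events make it less precise.

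**The case against.** The note can be read as a deliberate counting convention, set in advance and applied alike to both arms. The definition requires that no further acute intervention be felt necessary. An abdomen left open implies that another operation is expected, so the first operation may not have completed source control. The protocol does not say what else is done at closure, and Appendix 3 lists washout as an intervention in its own right. This stands in part. It is why an operation that closes the abdomen should still count when it includes a step that itself meets the definition. It does not bring closure alone within the definition, and it leaves no rule for abdomens left open before randomisation.

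Three stronger readings are tempting and are not supported:

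- **That such closures are often planned before allocation.** The protocol gives no frequency of open abdomens, no timing of closure, and no number still open at randomisation. It shows only that this can happen.
- **That the prior ICU trial cited in the Background (drainage in 19% v 9%) anchors the illustration.** That figure is for radiological drainage, which surgical closure cannot enter.
- **That the whole outcome is diluted.** The radiological count is untouched, and the expected difference in mean counts does not change.

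It is also fair that dropping every closure would go too far. A closure after an operation done because of failure after randomisation may depend on allocation and is real procedural burden. A site judgement on whether a closure was planned would add discretion in an open-label trial. Both points shape the fix.

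Finally, the SAP, which is not at hand, may hold an analysis without closures. But the protocol itself fixes the counting rule, so a SAP that follows it inherits the conflict.

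**Conclusion.** The point holds as a small correction to one secondary outcome. The counting note conflicts with the definition above it. Through the randomisation-based window, it lets closures of abdomens already open at allocation enter the surgical and any-type comparisons.

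The direction is clear provided such closures are unrelated to allocation: odds ratios, risk ratios and Pr(Y > 0) contrasts move towards no effect, the risk difference shrinks by the factor 1 − c, and power falls. The size cannot be established from the protocol. The risk ratios of 0.68 to 0.77 (from 0.63) and power of 82% to 67% (from 88%) rest wholly on assumed rates of 19% v 12% and assumed closure shares of 3% to 10%. If open abdomens at randomisation are rare, the effect is small. The power figures use a simple comparison of two proportions, not the planned covariate-adjusted mixed model, whose adjustment would absorb some of the variation.

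**What to change.** 1. In section 3.6, reconcile the note with the definition, and record abdominal closure as its own procedure type.
2. In section 10.2.4, state that the between-arm comparison and Pr(Y > 0) do not count a closure whose abdomen was left open at an operation dated before randomisation, unless the operation note documents a procedure that itself meets the source control definition. Operation dates and notes decide this, so no site judgement about intent is needed.
3. Keep counting closures that follow operations done after randomisation.
4. Report all closures descriptively by arm, and give the count with closures included as a sensitivity analysis.

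The cost is a short wording change, one extra recorded type and one extra analysis. No information is lost, because every closure is still reported. The change concerns outcome counting only and alters nothing in patient care.
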